The Keto-Mojo device requires a finger stick with a lancet, identical to those used to measure blood sugar, and uses only a small drop of blood. The device provides values within about 15 seconds following sampling. An alcohol prep will be used to cleanse the surface of the skin prior to each stick and a bandage will be applied to reduce risk of infection.

Participants will remain on all CF chronic care medications **and/or** standard exacerbation therapy (intravenous antibiotics and increased airway clearance throughout the course of the study. The study pharmacist will provide the ketone or placebo supplements by computer-generated random assignment in blocks of three participants and will have sole access to the randomization code.

Spirometry measurements, CRP, and, history/physical exam and Sputum bacteriology will be conducted at the beginning of hospitalization as part of standard of care (these results will be pulled from the medical record for study purposes. Spirometry measurements and history/physical exams will also be performed at the end of hospitalization as part of standard of care and will be pulled from the medical record for study purposes.

For outpatient subjects, these results will be pulled from the medical record and study procedures will also be performed at visit 1 and visit 2 as according to the consent

Spirometry will also be performed in addition to those for standard care just before the participant drinks the ketone supplement or placebo control and one hour after on day 1 and either day 5, 6 or 7.

Additional sputum and blood will be collected at baseline before the treatment and at patient-discharge for trial-specific readouts.

The participants will also be asked to complete the CFQR questionnaire and a food diary every night. They will also be asked to complete the symptom questionnaire on hour after receiving the morning ketone or placebo.

REQUIRED - SELECT ONE OR BOTH: Will this be a retrospective study and/or a prospective study?

Yes No * Retrospective

Yes No * Prospective

Yes No * Will the study involve the prospective collection or analysis of data, documents, or records?

Yes No * Will the study involve the prospective collection or analysis of biospecimens?

What is the expected end date of the study (including data analysis)?

* Provide the total number of subjects to be included at all sites, both retrospectively (including records) and prospectively.

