38. My child wheezed.....				
39. My child had trouble breathing.....				
40. My child woke up during the night because he/she was coughing.....				
41. My child had gas.....				
42. My child had diarrhea.....				
43. My child had abdominal pain				
44. My child has had eating problems				

Please be sure you have answered all the questions.

THANK YOU FOR YOUR COOPERATION!

Appendix 6

EForm Name: IRB EPORTFOLIO

Page: 31. ATTACHMENTS

Section:

Question: Clean Copy

File Name: questionnaire(symtom)220220.docx

SYMPTOM QUESTIONNAIRE**How is your general health today?** (Please check one box)

Very Good
 Good
 Fair
 Poor

Please record any symptoms you may have had today (tick one box for each symptom experienced)

Absent *I did not have this symptom at all*
 Mild *I had this symptom occasionally, but it didn't really bother me*
 Moderate *I had this symptom often, it bothered me quite a bit*
 Severe *I had this symptom very often, it bothered me a great deal*

	Absent	Mild	Moderate	Severe
Nausea				
Vomiting				
Heartburn				
Stomach Pain				
Diarrhea				
Constipation				
Bloating/Feeling of Fullness				

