Belching				

If you experienced any of the above symptoms, at what point after supplementation did they occur?

	Immediately	One hour	Two hours	Three or more hours
Nausea				
Vomiting				
Heartburn				
Stomach Pain				
Diarrhea				
Constipation				
Bloating/Feeling of Fullness				
Belching				

If you experienced any of the above symptoms, how long did they last? If applicable, please specify the number of times the symptom occurred.

	Less than 30 min	One hour	Two hours	Three or more hours
Nausea				
Vomiting				
Heartburn				
Stomach Pain				
Diarrhea				
Constipation				
Bloating/Feeling of Fullness				
Belching				

Final Day Question (only). Which study condition do you think you were in?

- Placebo condition (I **did not** drink the ketones)
- Ketone Condition (I **did** drink the ketones)

Additional Comments:

Appendix 7

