Adverse event rates (e.g. gastrointestinal distress or dizziness)	As they occur (cumulative reports also reviewed quarterly)
Serious Adverse Events	Immediate reporting (within 24 hrs) to IRB
Compliance to treatment	After every 5 patients that complete the study

Qualifications and responsibilities of Medical/Safety Oversight

[name] will serve as medical monitor for this study. [name] is an Assistant Professor of Medicine at UAB. He has conducted numerous CF-related clinical trials and has extensive experience serving as a Co-Investigator for NIH-funded studies. As Medical Monitor, [name] will review the reports sent by the project coordinator (at the frequency outlined above) to determine whether there is any corrective action, trigger of an *ad hoc* review, or stopping rule violation that should be communicated to the study investigator, UAB IRB, and NIH.

Measurement and reporting of participant accrual, adherence to inclusion/exclusion

criteria and site performance Review of the rate of participant accrual and adherence to pre-specified inclusion/exclusion criteria will occur after the recruitment of every five patients throughout the study. During this phase, the target is to enroll approximately five patients per quarter. No specific subgroups will be tracked. We envision a high retention rate as this study will be conducted in an inpatient setting and will have close follow-up in the outpatient cohort. The quarterly review will assess this enrollment rate as well as to assure that participants meet eligibility criteria as outlined in the grant proposal. To accomplish this, the study statistician will oversee the preparation of data tables summarizing recruitment and enrollment status and demographic characteristics. In the event that participant accrual rates fall below projected levels, the study investigators will convene a conference call to discuss potential strategies to modify the recruitment, screening, and/or enrollment protocols for future recruitment efforts and will report any requested changes to the UAB IRB, medical/safety officer, and NIH.

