Data integrity: All data will be collected by the study coordinator, [name], and inputted into ~~Excel~~ Redcap on secure UAB network. This data can be converted to other statistical analysis software. Relational logic checks, such as out-of-range values and internal inconsistencies, will be developed and automatically run in parallel with data entry. Double-data entry of study outcomes will be used to further minimize and detect entry errors. Statistical reports will be generated and include: 1) total number of participants screened, consented, and randomized on study entry and follow-up, and 2) a summary of demographic and baseline characteristics. This data will be password protected and only accessible by the PI and study coordinator.

Confidentiality: Every effort will be made to maintain the confidentiality of participant data by the investigator and the Institutional Review Board (IRB) to the extent permitted by law. All participants will be assigned subject ID numbers so personal health information (PHI) will not be used to identify participants.

Measurement and reporting of adverse events

We plan to collect adverse event data from all participants in both treatment conditions on a daily basis throughout the study. Potential symptoms include nausea, vomiting, lightheadedness, and abdominal pain. Participants who report clinically relevant adverse events will be immediately referred to the PI ([name]) and the Medical Monitor ([name]) for additional evaluation and referral as appropriate. After

randomization, should the PI and research team determine that continued participation is contraindicated, the participant may be withdrawn from the study. Given that this is minimally invasive study, we do not anticipate that withdrawals will be common.

Other risks for this study are also judged minimal. Exogenous ketones have been shown to stimulate insulin secretion leading to mild reductions in blood glucose. We do not anticipate more than a 5-7% decrease in circulating glucose and do not anticipate symptomatic hypoglycemia. In the event that a patient presents with symptomatic hypoglycemia, our Study Coordinator, [name], will contact [name] immediately.

Measurement and reporting of participant compliance to treatment protocol

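### The symptom questionnaire has no item for lightheadedness or dizziness, although the data safety monitoring plan names both

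*Protocol*

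**What the plan says.** Two parts of the Protocol bear on this.

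**The safety plan (Appendix 9).** Under the heading on measurement and reporting of adverse events, data are to be collected every day from everyone in both arms. The method is not named. The plan then lists what may be seen: "Potential symptoms include nausea, vomiting, lightheadedness, and abdominal pain". The table of review frequencies has a row that begins "Adverse event rates (e.g. gastrointestinal distress or dizziness"; such events are reviewed as they occur, with cumulative reports each quarter. Under statistical analyses and stopping rules, event rates are to be aggregated by randomized group.

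**The symptom form (Appendix 6).** It asks for general health that day and then instructs: "Please record any symptoms you may have had today (tick one box for each symptom experienced". The rows are nausea, vomiting, heartburn, stomach pain, diarrhea, constipation, "Bloating/Feeling of Fullness" and belching. Two further grids use the same rows. One asks "If you experienced any of the above symptoms, at what point after supplementation did they occur" and the other asks how long the symptoms lasted. The form closes with a field headed "Additional Comments". Section 1 (Methods) says when it is completed: "They will also be asked to complete the symptom questionnaire on hour after receiving the morning ketone or placebo".

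**The concern.** Acceptability and tolerability open the purpose statement in Section 1, and the safety plan hypothesizes that the supplement will be well tolerated. What can be said about tolerability depends on what participants are asked. A prompted symptom and a volunteered one are not ascertained alike: a ticked row returns an explicit answer, including *absent*, while an empty comments field may mean that nothing happened or that nobody thought to mention it.

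Here the safety plan names a symptom that the attached form does not ask about. A low count of lightheadedness set beside the counts of nausea or bloating would be hard to interpret, because the difference could reflect the form and not the supplement. The Continuing Review section already gives a preliminary statement that the product was tolerated without adverse effects. The documents do not say which records that statement rests on. If it rests mainly on this form, it carries less information about lightheadedness than about the gastrointestinal symptoms.

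**Working it through.** No sample-size or error-rate figure is involved. The check is an item-by-item match, followed by a search for other routes by which the symptom could be recorded.

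**Step 1. Match the safety plan's items to the form's rows.**

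| Named in Appendix 9 | Where | Row in Appendix 6 |
|---|---|---|
| Nausea | symptom list | yes |
| Vomiting | symptom list | yes |
| Abdominal pain | symptom list | yes, as stomach pain |
| Lightheadedness | symptom list | none |
| Gastrointestinal distress | review table | yes, several rows |
| Dizziness | review table | none |

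Of the four symptoms in the list, 3 have a row and 4 − 3 = 1 does not. Of the two examples in the review table, 2 − 1 = 1 has no row.

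**Step 2. Count the grids.** There are three grids (severity, onset, duration) of eight rows each, so 3 × 8 = 24 row entries. None is for lightheadedness or dizziness, and no grid has a row for other symptoms.

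**Step 3. Look for another structured item in the attached tools.**

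- The data sheet (Appendix 2) records ketone and glucose readings and spirometry, with space for comments and notes. It has no symptom item.
- The CFQ-R (Appendix 5) asks about gas, diarrhea, abdominal pain and eating problems over a two-week recall. It has no item on lightheadedness or dizziness.
- The food record (Appendix 7) covers diet only.
- The list in Section 31 shows no separate adverse event form.

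**Step 4. Look for other routes of capture.**

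- The comments field on the symptom form can hold the symptom as free text, but without a standard grade, onset or duration.
- The daily collection in Appendix 9 might ask about it, but the Protocol does not describe how that collection is done.
- Appendix 9 also mentions a safety report or checklist. It is described as a way to pass concerns to the investigators, statistician and safety officer, and its content is not shown.

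**Step 5. Draw the consequence.** If the daily collection does not ask about lightheadedness, its recorded frequency is the true frequency multiplied by the share of affected participants who volunteer it. For the eight gastrointestinal symptoms, each participant is prompted. The first will tend to fall short of the second whenever that share is below one. The documents give neither the frequency nor the share, so the shortfall cannot be given as a number.

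**A possible explanation.** The symptom form's file name is dated 220220 and the safety plan's 17 June 2022. This would fit a later list that was not carried back to an earlier form, but the documents do not say so.

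**The case against.** The strongest reply is that the symptom form is not declared to be the adverse event record. The safety plan promises daily collection from everyone and does not restrict it to this form, Section 26 has the principal investigator evaluate all adverse events as they occur, and the Drug Review Sheet adds weekly safety meetings. This stands, and it is why the point is conditional on what the daily collection asks. It does not remove the mismatch, because no other means of soliciting symptoms is described or attached.

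Several stronger readings are tempting, and the documents do not support them:

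- *The form cannot record the symptom.* It can, through the comments field. What is missing is a structured item.
- *This is the only daily solicited safety instrument.* It is the only attached symptom checklist. Even daily completion is an inference, though a reasonable one, from the wording about today and from the question reserved for the final day.
- *Lightheadedness is an expected effect.* The safety plan calls it potential, and Section 26 names only gastrointestinal effects of the supplement.
- *It is a marker of the glucose risk.* The safety plan does say "Exogenous ketones have been shown to stimulate insulin secretion leading to mild reductions in blood glucose", but it treats this among other risks and does not link it to lightheadedness. Glucose is measured directly around dosing, and symptomatic hypoglycemia has its own contact route.
- *Affected participants have no path to referral.* Any participant who reports a clinically relevant event is referred, whatever the symptom. Only the checklist prompt is absent.
- *The comparison between arms is biased.* Section 12 describes the trial as double blinded and both arms use the same form. Nothing shows that under-reporting would differ by arm.

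**Conclusion.** The mismatch is confirmed: one of the four symptoms listed in the safety plan, which is also one of the two examples in its review table, has no structured item on the attached symptom form or on any other attached tool. The likely consequence is that lightheadedness or dizziness would be understated in both arms relative to the prompted gastrointestinal symptoms, and would lack comparable severity, onset and duration.

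This rests on two assumptions: that the undescribed daily collection does not itself ask about the symptom in a standard way, and that some affected participants would not volunteer it. If the first is wrong, what remains is only that the Protocol does not say how the question is put.

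The effect is confined to the description of tolerability and to the event rates aggregated by arm. The primary outcome (pulmonary function), the sample size and the error rates are not touched. The point is modest in weight but worth correcting, because tolerability is a stated purpose and the correction is small.

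**What to change.** Add a row for *Lightheadedness / dizziness* to the severity, onset and duration grids of the symptom questionnaire in Appendix 6, so that the form covers every symptom in the safety plan's list. If the daily adverse event collection already asks about it, say so in Appendix 9 and give the wording used.

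For participants who completed the form without this row, report the symptom as volunteered only, show it apart from the solicited symptoms, and do not pool it with answers from the revised form.

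The cost is one line in each of three grids and a minor IRB modification. Preliminary results already exist, so some participants have passed through on the present form. For them, solicited data on this item cannot be recovered. If enrollment is complete, the separate reporting is the part that still applies.

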METHODS: Describe the procedures for all aspects of your protocol. Tell us what you are doing.

Participants will be recruited by the Principal Investigator or Study Coordinator from the inpatient and **outpatient** CF population at UAB. Following admission to UAB Hospital for a routine CF exacerbation, **or within the outpatient setting**, the Study Coordinator will discuss the study with participants and obtain written informed consent before initiating the study.

Patients will be randomly allocated in unbalanced numbers (2:1) (n = 15 ketone and n = 8 control) to receive a ketone monoester or an identical-tasting placebo, respectively, for 8 days during the course of hospitalization for treatment of acute pulmonary exacerbation (One, 60 mL bottle of either a ketone ester will be consumed twice daily (30 mL or 15.0 g per dose) (KE4, KetoneAid, Falls Church, VA; 15.0 g or placebo (PL, flavored to closely match taste of the ketone) will be administered following an overnight fast and again at 1500h.

Participants will be **asked to drink about 1 fluid ounce of the ketone or placebo supplement twice a day (once in the morning and once mid-late afternoon) for up to 7 days. Each day in the study, the participant will be asked to fast overnight for about 8 hours before drinking the first dose of ketone or placebo. Following administration of the first dose of either the ketone or placebo and on either day 5, 6, or 7 a small drop of blood will be obtained from their finger before (time 0 min) and 15, 30, 60, 90, and 120 min after drinking the supplement. On days in between visit 1 and visit 2, we will check their blood sugar before drinking the supplement and 30 minutes after they drink the supplement. We will use a commercially available ketone meter (Keto-Mojo, Napa, CA) that provides a rapid assessment of blood ketone and glucose (sugar) levels. The Keto-Mojo device requires a finger stick with a lancet, identical to those used to measure blood sugar, and uses only a small drop of blood. Patients will be educated on how to use the device and self measure ketone and blood sugar.**

Blood sampling will occur from their indwelling catheter or **venipuncture** at day 1 and at day 5, 6, or 7 before administration of the ketone or placebo. We will try to coordinate this with any blood sampling done for clinical care.

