If the patient can expectorate additional sputum will be collected at visit 1 and visit 2

How will biospecimens be obtained, processed, distributed, and stored?

Blood samples will be collected from participants after signing informed consent. Samples will be stored and processed in [name] laboratory ([name]) for subsequent analysis.

How will biospecimens be labeled (e.g., unique identifier, medical record number, social security number, name, date of birth)?

Specimens will be labeled with a participant code and the date of the sample. The participant code will be a randomly assigned, unique alphanumeric identifier

How will clinical data associated with the biospecimens be collected and stored?

Clinical data will be collected and stored using the same alphanumeric identifier as described above and will be entered into a secure database maintained on a firewall- and password-protected network drive

What participant identifying information will be collected and linked to the biospecimens?

Samples will be labeled with a participant code and the date of the sample. Information which would reveal the identity of a participant code number or link data to an individual will be extremely limited.

What steps will be taken to maximize the confidentiality of linked identifiers? For example, procedures could include using a password-protected computer database to link identifiers, with limited personnel knowledgeable of the password, or coded identifiers released without the ability to link to clinical data (also called "stripped" or "anonymized" biospecimens).

Confidentiality of all participants will be fully protected and investigators will only use unique identifier numbers for labeling study samples and for compiling data files. Access to participant data will be strictly limited under control of the PI. Any publication of these data will not identify the participant by name.

Describe how the above numbers were determined (e.g., provide a power analysis, explain the pilot data, or reference prior studies.

Allocation of participants in a 2:1 (ketone:placebo control) fashion in blocks of 3 was chosen because this is a pilot study designed to provide preliminary data for an extramural grant. Descriptive statistics will be calculated for all quantitative measures, including assessments of acceptability and tolerability. We will have the appropriate number of patients available to address our questions.

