This randomized controlled trial (RCT) aims to evaluate the effectiveness of a commercially available ketone supplement on pulmonary function and markers of inflammation and metabolic health in patients with cystic fibrosis (CF) admitted for acute pulmonary exacerbation and a cohort of stable outpatient CF subjects. To accomplish this goal, a 5-7 day RCT will be conducted to compare the effects of ketone supplementation to a placebo control. The primary outcome will be differences in pulmonary function, namely FEV1.0, FVC, and FEV1.0/FVC. Secondary outcomes will include quantitative assessment of circulating insulin, glucose, and a number of inflammatory markers associated with the NLRP3 inflammasome. Qualitative assessment of tolerability and the feasibility of delivery will also be extensively examined. Compared to placebo control and standard care, we hypothesize that the ketone ester (KE4, KetoneAid, Falls Church, VA) will produce greater reductions in markers of inflammation and improvements in pulmonary function. We further hypothesize that ketone supplementation will be well-tolerated and prove to be feasible as it relates to administration and consumption of the ketone. Of note, this Ketone supplement is considered GRAS and does not require FDA IND or FDA oversight.

The intervention and measurement protocols pose minimal risk to participants (as described below). Because of this low-risk status, the data safety monitoring plan (DSMP) for this trial focuses on close oversight by Medical Monitor, [name]. We will also provide prompt reporting of excessive adverse events and any serious adverse events to the Cystic Fibrosis Center, IRB at the University of Alabama at Birmingham (UAB) and NIH. The data safety monitoring plan (DSMP) outlined below will adhere to the protocol approved by the UAB IRB.

Safety reports will be sent to the study statistician, the MPIs, and to medical oversight at the schedule specified below in the table. The project coordinator will be responsible for assembling the data and producing these reports, as well as assuring that all parties obtain copies of these reports. The frequency of data review for this study differs according to the type of data and can be summarized in the following table:

Data type	Frequency of review
Subject accrual (adherence to protocol regarding demographics, inclusion/exclusion)	After every 5 patients that complete the study

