Once randomized participants begin the intervention, data on treatment adherence will be monitored by research staff on an ongoing basis. Adherence will be measured as the number of times the participant consumes the placebo or ketone supplement. Adherence will be reviewed after every 5 participants or quarterly (whichever comes first) and if the safety officer has concerns about whether compliance has reached a level that might inhibit the ability of the study to test its primary hypotheses, he will suggest a conference call for study investigators to discuss methods for improving compliance.

Statistical analyses and stopping rules

Although no formal power analysis was conducted for this study (due to exploratory nature of the study as pilot and feasibility), our 2:1 (ketone:placebo) recruitment strategy will provide opportunity to detect smaller differences in the ketone treated group. We plan for no interim efficacy analyses and will not unblind until recruitment is complete. In this minimal-risk study, it is more likely that drop-outs or difficulty in recruiting adequate numbers of participants will require stopping the trial than that excess adverse events will occur and require stopping the trial. However, as outlined elsewhere, we will monitor adverse event rates in all participants and aggregate by randomized group. The safety officer, together with the PI, will alert the UAB IRB and the NIH if a larger than reasonably expected adverse event rate should occur in either treatment condition. Other issues relating to stopping rules for this trial include:

New Information

It is exceedingly unlikely that any new information will become available during this trial that would necessitate stopping the trial.

Limits of Assumptions

It is possible that baseline differences between the groups, excessive study dropouts, and/or missing data by the interim measurement time points will limit the value of data analysis of measurements. Baseline differences will be evaluated and effects on the power to detect differences in the primary outcome will be evaluated and communicated to the PIs, and safety office. Given the monitoring plans outlined elsewhere in this document as well as the randomized design of this study, it is exceedingly unlikely that there will be baseline differences between groups of any magnitude to threaten the validity of the study.

Limits of Rules

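### Is the data safety monitoring plan wrong to say that 2:1 allocation helps to detect smaller differences?

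*Protocol*

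**What the plan says.** The sentence stands in the data safety monitoring plan (Appendix 9 to section 31), under Statistical analyses and stopping rules. It opens "Although no formal power analysis was conducted for this study (due to exploratory nature of the study as pilot and feasibility" and goes on to say that "our 2:1 (ketone:placebo) recruitment strategy will provide opportunity to detect smaller differences in the ketone treated group". The plan attaches no significance level, power, effect size or SD to it.

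The Introduction of the same appendix says that "a 5-7 day RCT will be conducted to compare the effects of ketone supplementation to a placebo control" and that "The primary outcome will be differences in pulmonary function, namely FEV1.0, FVC, and FEV1.0/FVC". It states two hypotheses: one of benefit relative to placebo and standard care, and one that the ketone will be well tolerated and feasible to give.

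Section 1, Methods, fixes the numbers: "Patients will be randomly allocated in unbalanced numbers (2:1) (n = 15 ketone and n = 8 control". Section 9 says that the 2:1 ratio "was chosen because this is a pilot study designed to provide preliminary data for an extramural grant", and plans descriptive statistics that cover acceptability and tolerability. The purpose statement in section 1 names acceptability and tolerability first.

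**The concern.** The sentence follows directly on the admission that there was no power analysis, so it reads as partial compensation for it. It is also the only remark in the document on what size of difference could be detected. The same appendix later says, under Limits of Assumptions, that "effects on the power to detect differences in the primary outcome will be evaluated", so a reader has the between-arm primary outcome in mind.

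For a between-arm comparison of means with equal SDs and a fixed total, moving away from an equal split widens the standard error. Read that way, the sentence has the direction wrong. The study is meant to feed a grant application, so the idea that 2:1 sharpens the placebo comparison could be carried into the next design. The reading on which the sentence is true points to change within the ketone arm. In inpatients, spirometric or inflammatory change in that arm is mixed with the response to "standard exacerbation therapy (intravenous antibiotics and increased airway clearance throughout the course of the study", and cannot be credited to the ketone without the placebo arm.

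**Working it through.** The document gives no detectable difference, so there is no stated figure to reproduce. The only numerical input from it is 15 ketone and 8 control (section 1, Methods), total 23. Assumed: two-sided 5%, 80% power, equal SDs in the two arms, and a t-test unadjusted for baseline.

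**Between arms.** The detectable difference is proportional to SD × sqrt(1/n1 + 1/n2).

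- 15 v 8: sqrt(1/15 + 1/8) = sqrt(0.1917) = 0.4378
- 12 v 11: sqrt(1/12 + 1/11) = sqrt(0.1742) = 0.4174
- Ratio: 0.4378 / 0.4174 = 1.049

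Both splits have 21 degrees of freedom, so this ratio does not depend on the significance level, the power or the SD. The noncentral t distribution gives:

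| | 15 v 8 | 12 v 11 |
|---|---|---|
| Detectable difference, 80% power | 1.286 SD | 1.226 SD |
| Power at a true difference of 1 SD | 58.7% | 62.7% |
| 95% CI half-width | 0.910 SD | 0.868 SD |

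Adjusting for baseline with correlation r multiplies the SD by sqrt(1 − r²), with 20 degrees of freedom. The detectable differences become 1.117 v 1.065 SD at r = 0.5, and 0.921 v 0.878 SD at r = 0.7. The ratio is still 1.049.

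**Within the ketone arm** (one-sample t on change, in SDs of change).

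- n = 15: 0.778 SD
- n = 12: 0.889 SD
- Ratio: 0.778 / 0.889 = 0.875, about 12% smaller

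**When the between-arm direction reverses.** Let k be the ketone SD divided by the placebo SD. The two splits are equal when k²/15 + 1/8 = k²/12 + 1/11. This gives k²/60 = 3/88, so k² = 2.045 and k = 1.43. Above that ratio 15 v 8 is the better split, but nothing in the document suggests so large a ratio. The direction also reverses if the comparator is a smaller trial with 8 per arm: sqrt(1/8 + 1/8) = 0.5000, detectable difference 1.507 SD. That gain comes from the extra participants, not from the ratio.

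**Source of the low sensitivity.** At a total of 23, an equal split improves the detectable difference by 1.286 − 1.226 = 0.060 SD. The remaining 1.226 SD reflects the small total.

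**The case for a change.** The strongest case for changing the sentence is that it offers the allocation ratio in place of a power analysis, in a trial whose aim and primary outcome are a contrast with placebo. For that contrast the ratio is a cost under the usual assumptions. Leaving 2:1 in place while restating its rationale would take one paragraph, and the reader would learn what 15 v 8 can show.

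Much of this stands. The arithmetic is right, the sentence does not separate within-arm from between-arm precision, and it should not be read as a gain against placebo.

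It does not make the sentence false, because the sentence names the ketone-treated group and is correct for that group. Precision there has a stated use. Tolerability, acceptability and feasibility are aims of the study, and blood ketone and glucose are measured serially after dosing. The mixing with exacerbation therapy bears on spirometry and inflammation in inpatients. It matters much less for those other aims, and does not arise in the same way in the stable outpatient cohort. Nothing in the document says that efficacy will be judged on change within the ketone arm; the Introduction to the monitoring plan sets it against placebo.

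An added rule that efficacy rests on the ketone-placebo difference would only repeat what is already there. A detectable-difference statement would rest on a significance level, power and test that the document does not give.

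**Conclusion.** No change is called for. The sentence is loosely placed and could be misread, but it is true for the group it names and contains no figure to correct. Misreading it would overstate sensitivity for the placebo comparison by a small amount: about 5% in the detectable difference, or about 4 percentage points of power at a true difference of 1 SD. Those sizes assume a fixed total of 23, equal SDs and, for the power figures, a two-sided 5% unadjusted t-test. A 2:1 ratio is a fair trade-off in a pilot that also wants tolerability and feasibility data on the supplement. A trial run exactly as written would enrol the same participants, analyse the same contrast and reach the same results whether or not the sentence were reworded, so the rewording has no gain.
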